### 6.1.2 Sample size calculations for immunogenicity

To address the humoral immunogenicity endpoints, the analysis will compare the area under the magnitude-breadth curve of the IgG Env binding Ab response, and will compare the frequency of memory B cells that bound to gp120CH505 TF but not to gp120CH505 TF  $\Delta$ 371, 2 weeks after the third (Part A) or fourth and sixth (Part B) vaccinations with CH505TF gp120. To estimate power, binding magnitude-breadth data were simulated assuming that the proportion of non-zero responses was 0.94 in both comparison groups. This is based on pilot data for the IgG binding Ab response in HVTN 088. For these calculations, non-zero responses, modeled on the  $\log_{10}$  scale, were drawn from a normal distribution. The mean non-zero response in group 1 was set to 4.06. This was the mean non-zero response in the HVTN 088 vaccine arm T2 (the treatment arm for vaccine naïve participants). The standard deviation (SD) of the non-zero response was set to 0.391 for both groups; this was the SD of the non-zero response in the HVTN 088 vaccine arm.

The differential binding rate is the fraction of class memory B cells that have the property of binding the two protein hooks in a differential manner (defined by flow gating). In the assay, two measurements are made simultaneously: binding to the transmitted founder CH505 virus, and binding to the  $\text{I}\Delta 371$  variant. Each of these yields a measurement of the proportion of memory B cells that bind to a target virus. While the primary interest is in the differential binding to these two viruses, which is the difference of these proportions, we will also evaluate each measure separately to further describe and explore the relationship between these measures under the scenarios represented by the arms of this trial.

Power for this is high if we can pool the cells across participants, which would be possible under an assumption of a homogeneous rate of differential binders across participants within a treatment group. Our prior expectation is that this is at least approximately correct, though we will evaluate the homogeneity and if we find evidence for different rates across participants, we will revert to the more conservative approach of treating participant rates of differential binders as varying across participants around a common group mean. In case pooling is not justified, power is the same (on the per-SD scale) to that calculated for binding Abs, since preliminary data indicate that the log-transformed rates of differential binding are consistent with the normal distribution.

However, interpretation of these SDs differs between the differential binding rate power calculations and the power calculations for the primary antibody endpoints. In the case of binding Abs, the SDs are on the scale of log-transformed binding Ab response values (which are areas under the magnitude-breadth curve), so it is reasonable to describe these in terms of "fold changes". However for differential binding Abs, the values and SDs are fractions. So for instance, if the SD is .001 (equivalently, 0.1%) that means that there is 90% power to detect a 0.2% difference between the differential binding rates in the two arms. In the text below we provide example interpretations of the SDs for the context of the primary Ab binding endpoints only.

To address antibody endpoints in Part A, the analysis will descriptively summarize binding response positivity call rates, and test superiority of the frequency of differential memory B cell binding (to wild type vs mutant  $\text{I}\Delta 371$  CH505) and of the magnitude and breadth of the IgG binding Ab response to a panel of gp120 proteins for each of 2 comparisons (Group 1 vs 2, and Group 2 vs 3), using a two- sided Wilcoxon rank sum test with 5%/2 type-I error rate per comparison. The sample size of 12 vaccinees per group will give 80% power to detect a true difference of 1.81 standard deviations (SDs) between the mean responses and 90% power to detect a true difference of 2.04 SDs. Using the mean and SD values from the HVTN 088 trial, the difference of 1.81 SDs translates to a difference of 0.708 units of  $\log_{10}$  binding magnitude; if 1 of the comparison groups has the same mean as was seen among non-negative values among vaccine recipients in the HVTN 088 trial (4.06 units), then after incorporating the expected 6% zero-valued (negative responder) measures, this corresponds to observing an increase or decrease in the overall mean from 3.691 in group 1 to 4.336 in group 2. These calculations assume a 10% loss-to-follow-up rate and the (94%) response rate observed in the HVTN 088 vaccine recipients. The same approach will be used to test superiority of the magnitude of the IgG binding Ab response to each individual gp120 antigen in the panel.

To address antibody endpoints in Part B, the analysis will descriptively summarize binding and neutralization response positivity call rates and test superiority of the frequency of differential memory B cell binding and of magnitude and breadth of the IgG

binding Ab response to a panel of gp120 proteins and of the neutralization of tier 1 and tier 2 panels of HIV-1 viruses. Each analysis will be conducted separately for each of 2 pooled comparisons (additive vs sequential, pooling over groups with and without mosaic DNA: Groups 5 and 6 combined vs Groups 7 and 8 combined; effect of mosaic DNA, pooling over groups receiving additive and sequential proteins: Groups 5 and 7 combined vs Groups 6 and 8 combined), and for each of 6 pairwise comparisons among these groups using a two- sided Wilcoxon rank sum test with 5% type-I error rate per pooled comparison and a 5%/6 type-I error rate per pairwise comparison. The sample size of 20 vaccinees per group will give 80% power to detect a true difference of 1.63 standard deviations (SDs) between the mean non-zero responses and 90% power to detect a true difference of 1.81 SDs for the pairwise comparisons. Using the mean and SD values from the HVTN 088 trial, the difference of 1.63 SDs translates to a difference of 0.637 units of  $\log_{10}$  binding magnitude; if 1 of the comparison groups has the same mean as was seen among non-negative values among vaccine recipients in the HVTN 088 trial (4.06 units), then after incorporating the expected 6% zero-valued (negative responder) measures, this corresponds to observing an increase or decrease in the overall mean from 3.609 in group 1 to 4.175 in group 2. The sample size of 40 vaccinees per pooled group will give 80% power to detect a true difference of 0.80 standard deviations (SDs) between the mean non-zero responses and 90% power to detect a true difference of 0.90 SDs (these 2 are each conducted at a 5% alpha level). Using the mean and SD values from the HVTN 088 trial, the difference of 0.80 SDs translates to a difference of 0.313 units of  $\log_{10}$  binding magnitude; if 1 of the comparison groups has the same mean as was seen among non-negative values among vaccine recipients in the HVTN 088 trial (4.06 units), then after incorporating the expected 6% zero-valued (negative responder) measures, this corresponds to observing an increase or decrease in the overall mean from 3.722 in group 1 to 4.007 in group 2. These calculations assume a 10% loss-to-follow-up rate and the (94%) response rate observed in the HVTN 088 vaccine recipients. The same approach will be used to test superiority of the magnitude of the IgG binding Ab response to each individual gp120 antigen in the binding panel.

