chosen for the dose in the arms of Part B will be determined by analysis of antibody binding data from a validated assay and will additionally be informed by the assay of memory B-cell receptor binding to CH505TF gp120 and differential binding to the CH505 I $\Delta$ 371 gp120 Env. Preliminary data from the NHP 106 study included both plasma antibody and flow cytometric quantification of memory B cells that displayed differential binding; analysis of both measures indicated that 300 mcg/dose was optimal in NHP. For that reason, we expect that the validated assay primary outcome data and the secondary outcome data from flow cytometry will give a concordant answer.

**Figure 4-12. Inhibition of CH106 CD4 bs binding to B.63521 gp120 Env by NHP 106 plasma from immunization with 5 different doses of CH505TF gp120.**

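### The plan gives two units of analysis for differential-binding memory B cells, and its rule of pooling cells unless heterogeneity is found can raise the Part A error from 2.5% to about 4 to 4.5% under moderate heterogeneity

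*Combined protocol and SAP*

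**What the plan says.** The endpoint is the frequency of memory B cells that bind CH505 TF gp120 but not the mutant lacking isoleucine 371. It is secondary endpoint 1 in Part A (section 5.2). Section 4.8.1, in the text on the macaque dose-ranging study, says the Part B dose is determined by binding antibody data and "will additionally be informed by the assay of memory B-cell receptor binding to CH505TF gp120 and differential binding".

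Section 6.1.2 describes its analysis in two places.

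- **Cells pooled by expectation.** "Power for this is high if we can pool the cells across participants, which would be possible under an assumption of a homogeneous rate". The authors expect this to hold at least approximately, will check it, and say that "if we find evidence for different rates across participants, we will revert to the more conservative approach", which lets participant rates vary around a group mean. Without pooling, power is said to equal that for binding antibodies per SD, because "preliminary data indicate that the log-transformed rates of differential binding are consistent with the normal distribution".
- **Participants compared by rank test.** For Part A, this frequency is tested for Group 1 vs 2 and Group 2 vs 3 "using a two- sided Wilcoxon rank sum test with 5%/2 type-I error rate per comparison", with power given per vaccinee. For Part B the same test is used with "5% type-I error rate per pooled comparison and a 5%/6 type-I error rate per pairwise comparison".

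The plan does not name the homogeneity test, its level, the number of cells per participant, the test used after pooling, or a figure for the high power.

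**The concern.** A Wilcoxon test on one frequency per participant cannot use pooled cells, so the two descriptions are different analyses. The power described as high belongs to the pooled one, which the statement of tests does not name.

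Pooling treats each cell as an independent replicate. Randomization was by participant, so the variance of an arm mean includes between-person variance that the pooled test leaves out. The safeguard is a pretest in about 22 people, and a pretest that fails to reject does not show that this variance is zero. Moderate variation is often missed, and the pooled test is then run when its p-values are too small.

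At stake is a false difference between dose arms on an endpoint that feeds, in a supporting role, into the Part B dose choice, and between regimens when the comparison recurs in Part B.

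**Working it through.** **Inputs from the plan.** 12 per arm in Part A with 10% loss, so 11 evaluable; two-sided alpha 0.025. In Part B, 18 evaluable per arm at 0.05/6 = 0.0083, and 36 per pooled arm at 0.05. Non-zero binding responses have mean 4.06 and SD 0.391 (log10), with 94% non-zero.

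**Assumed, because the plan is silent.** Chi-square homogeneity test at 5% (varied from 1% to 10%); about 5,000 cells per participant at a 0.1 to 0.2% rate; a two-proportion z-test after pooling; lognormal participant rates with coefficient of variation CV.

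**1. The plan's own power.** The stated overall mean implies one zero among 11: 4.06 × 10/11 = 3.691. With that, the simulated Wilcoxon test has 79.7% power at 1.81 SD (stated 80%) and 89.7% at 2.04 SD (stated 90%). Part B pairwise gives 80.0% at 1.63 SD and 90.1% at 1.81 SD; Part B pooled arms give 81.0% at 0.80 SD and 89.6% at 0.90 SD. These figures reproduce, and they describe the participant-level test. The power attributed to pooling has no number to reproduce.

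**2. What pooling does under the null.** Let μ = cells × rate be the expected binders per participant. Counts have overdispersion φ = 1 + μ·CV². The pooled z-statistic then has variance φ, so its error at alpha 0.025 is about 2Φ(−2.241/√φ).

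**3. Error of the rule as written.** The rule was simulated with 6,000 to 20,000 trials per setting: homogeneity test within arms on 2 × (11 − 1) = 20 df, pooled test if not rejected, otherwise Wilcoxon. The Monte Carlo standard error at 6,000 trials is √(0.043 × 0.957/6,000) = 0.26 points, so part of the spread below is noise.

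| Cells, rate, CV | μ | φ | Pooled test alone (formula) | Rule as written |
|---|---|---|---|---|
| 5,000, 0.2%, 0 | 10 | 1.0 | 2.5% | nominal |
| 5,000, 0.2%, 20% | 10 | 1.4 | 5.8% | 4.0 to 4.7% |
| 5,000, 0.1%, 30% | 5 | 1.45 | 6.3% | 4.0 to 4.5% |
| 5,000, 0.2%, 30% | 10 | 1.9 | 10.4% | 4.2 to 4.3% |
| 5,000, 0.2%, 50% | 10 | 3.5 | 23% | about nominal (2.3%) |
| 20,000, 0.2%, 30% | 40 | 4.6 | 30% | 2.0 to 2.1% |

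The Wilcoxon test used alone stays at about 2.0 to 2.4%. As a hand check on the second row, the homogeneity test missed the variation in 69% of trials, so the pooled branch alone contributes about 0.69 × 5.8% = 4.0%. In the last two rows heterogeneity is nearly always detected: pooling is chosen in about 4% and at most 0.3% of trials.

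Over a wider grid (μ from 5 to 500), the Part A maximum is 4.2 to 4.5% at φ of 1.5 to 1.75, or 1.7 to 1.8 times nominal. With the homogeneity test at 10% or 1%, the maximum is about 1.4 or 2.4 times nominal.

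**4. With an overall test first.** Section 6.4.4.1 says pairs are compared only after a significant overall test at 0.05, with an exemption for pre-specified comparisons. Behind a participant-level Kruskal-Wallis gate, the three moderate settings give 1.8 to 2.2%.

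**5. Part B, no gate.** Pairwise comparisons reach about 1.4 to 1.7% against 0.83%. Pooled-arm comparisons reach about 6% against 5%.

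**6. Power when rates are truly homogeneous.** For a 1.5-fold difference (5,000 cells, 0.2%, 11 per arm): pooled test 86%, the two-stage rule 84.5%, Wilcoxon 77%.

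**7. The fallback power.** Without zeros, the Wilcoxon test with 11 per arm has about 93 to 94% power at 1.81 SD and reaches 80% near 1.45 to 1.5 SD. Calling the power the same therefore carries the binding assay's zeros over to a different assay. The scale also shifts. Normality is argued on log-transformed rates, but the worked example reads the SD as a raw fraction: 2.04 × 0.1% = 0.2%.

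**The case against.** The strongest reply is that the text on pooling is sample-size commentary. Section 6.4.4, which governs analysis, contains no cell-pooling test. All numerical power is participant-level, no sample size rests on the word high, and the claim is openly conditional with a fallback given. That stands: a reader might infer that power was misattributed or concealed, and the plan does not support that. It remains true that 6.1.2 states a rule for choosing the analysis, and nothing in 6.4.4 withdraws it.

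The gate in 6.4.4.1 also matters. If it applies, Part A error stays below nominal in every setting checked. Whether it applies is unclear, because the comparisons in 6.1.2 could count as pre-specified and so be exempt.

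Three stronger readings should be resisted.

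- **Error of 20% or more.** Those figures come from always pooling. The plan would not do that, because heterogeneity of that size is almost always detected.
- **The normality remark contradicts pooling.** Observed rates vary through binomial sampling even under one common rate, and their logs can look normal. The remark does not establish between-person variance.
- **A false result would set the Part B dose.** The endpoint is secondary and only adds to the validated binding data.

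**Conclusion.** The inconsistency is certain: one endpoint has two units of analysis, and the choice between them is left to an unspecified pretest. The pretest rule is also not a safe default. In Part A it can raise the per-comparison error from 2.5% to about 4 to 4.5%.

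That figure is conditional on a 5% chi-square homogeneity test, about 5,000 cells per participant at 0.1 to 0.2%, heterogeneity in the moderate band (φ roughly 1.4 to 1.9), and no overall-test gate. There is little or no inflation if rates are homogeneous, if φ is about 3 or more, or if the gate applies, and the effect is slight for the Part B pooled arms. A reader might infer that the error rate nearly doubles in general. It does so only as a worst case under these assumptions, none of which the plan fixes. If the Wilcoxon test alone governs, error is controlled, but the statement about high power then has no analysis to attach to.

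**What to change.** In section 6.1.2, delete the sentence on high power from pooling and the rule that pools unless heterogeneity is found. State that the participant is always the unit of analysis: one differential-binding frequency per participant, compared with the Wilcoxon tests already named there. If cell counts are to be used, specify a beta-binomial or quasi-binomial model that always keeps participant-level overdispersion and is never simplified by a pretest. Pooled-cell summaries can stay as description.

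State this endpoint's power on one named scale (log or raw fraction), with its own assumption about zeros, instead of borrowing the binding antibody figures. Say in 6.4.4.1 whether the overall test precedes these comparisons.

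The change is wording only and needs no new data; it should be made before any unblinded analysis of this endpoint. The cost is the loss in step 6 if rates really are homogeneous: from 86% for the pooled test, or 84.5% for the rule as a whole, to about 77%.

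### Section 6.1.2 gives two conflicting units of analysis for differential binding, pooled cells or participants, and its power example moves a log-scale result onto raw fractions

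*Combined protocol and SAP*

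**What the plan says.** Everything quoted here is in Section 6.1.2 of the combined protocol and SAP.

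**Unit of analysis.** The text opens with "Power for this is high if we can pool the cells across participants", which requires one common rate within each group. It continues "Our prior expectation is that this is at least approximately correct, though we will evaluate the homogeneity", and then says "if we find evidence for different rates across participants, we will revert to the more conservative approach", meaning that participant rates would be treated as varying around a group mean. No homogeneity test, threshold or pooled-cell test statistic is given. The next paragraphs set the superiority test for this same endpoint. In Part A it is a two-sided "Wilcoxon rank sum test with 5%/2 type-I error rate per comparison" with 12 vaccinees per group. In Part B it is the same test at 5%/6 per pairwise comparison with 20 per group. Section 6.4.4.1 also describes arm comparisons at participant level.

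**Scale.** Per-SD power is carried over from binding antibodies because "the log-transformed rates of differential binding are consistent with the normal distribution". The next paragraph says "However for differential binding Abs, the values and SDs are fractions", and converts an SD of 0.1% into 90% power for a 0.2% difference.

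**Endpoint.** Sections 5.2 and 6.1.2 describe a gated frequency of differential-binding memory B cells. Section 6.1.2 also describes the quantity of interest as binding to one target minus binding to the other, "which is the difference of these proportions".

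**The concern.** Vaccine groups are assigned to people, so people are the independent units. A test that counts pooled cells is valid only if every participant in a group has the same true rate. An unspecified look at homogeneity in about 11 people per arm has limited power to find moderate differences between them. Where it misses them, the pooled p-value is too small. The plan does not say whether this rule or the Wilcoxon test governs.

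The scale problem is separate. If log rates are normal with a common SD, the detectable effect is a ratio and does not translate into a fixed absolute difference. A reader planning around 0.2 percentage points could then be misled about what the trial can detect.

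The result is used before Part B opens: Section 4.8.1 lists this assay as an additional input to the Part B protein dose.

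**Working it through.** **1. The plan's own power.** The stated overall mean of 3.691 equals 4.06 × 10/11. This implies 11 evaluable per group (12 less 10%), with 10 non-zero and 1 zero. A simulated two-sided Wilcoxon test at 0.025 with those inputs gives 80.1% at 1.81 SD and 89.8% at 2.04 SD, so the stated 80% and 90% reproduce. The example is 2.04 × 0.1% = 0.204%, which is correct arithmetic on the raw scale.

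**2. Type I error of the switch, Part A.** The documents give no cell counts, between-person variation or homogeneity test, so these are assumptions:
- 11 per arm and the same distribution of rates in both arms.
- Log-normal participant rates with coefficient of variation CV (log variance = ln(1 + CV²)) and Poisson cell counts.
- Homogeneity checked in each arm by X² = Σ(xᵢ − x̄)²/x̄ on 10 df.
- If neither arm rejects, a pooled two-proportion z test on cells; otherwise Wilcoxon on participant rates. Both are at a nominal 2.5%.

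| Differential cells per person, CV | Pooling kept (5% threshold) | Error, 5% threshold | Error, 1% threshold |
|---|---|---|---|
| Homogeneous rates | usually | 2.1-2.4% | no inflation |
| 5, 30% | 59% | about 4% | 5-6% |
| 10, 30% | 30% | 3.9% | 5-6% |
| 20, 20% | 34% | 3.9% | 5-6% |
| 100, 10% | 23% | 3.5% | 5.7% |
| 100, 20% | 0.2% | 2.2% | 2.3% |

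Across repeated runs, the moderate-heterogeneity cases lie at about 3.4-4.2% (5% threshold) and 5-6% (1% threshold). Wilcoxon used throughout gives 1.8-2.4%. In Part B pairwise comparisons (18 evaluable, nominal 0.83%) the switch reaches about 1.6% and 2.3%, and Wilcoxon alone gives 0.5-0.8%.

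**3. The power example on the log scale.** Take log-normal rates, a reference-arm raw SD of 0.1%, a common log-SD, and one zero responder in 11 per arm. For an assumed mean rate m (in %):
- log-SD: σ = √ln(1 + (0.1/m)²)
- shift for +0.2 points: ln(1 + 0.2/m)/σ log-SDs
- fold change at 2.04 log-SDs: exp(2.04σ)

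| m | σ | Shift (log-SDs) | Power | Fold change for 90% power |
|---|---|---|---|---|
| 0.05% | 1.269 | 1.27 | 42% | 13.3 |
| 0.1% | 0.833 | 1.32 | 45% | 5.5 |
| 0.2% | 0.472 | 1.47 | 57% | 2.6 |
| 0.3% | 0.325 | 1.57 | 65% | 1.9 |
| 0.4% | 0.246 | 1.65 | 71% | 1.7 |

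The powers agree between simulation runs to within about two points. Every shift is below the 1.81 that the plan needs even for 80%. At m = 0.05%, 90% power needs about 0.05 × (13.3 − 1) = 0.62 points, not 0.2.

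**4. Endpoint definition.** A difference of two proportions can be zero or negative and then has no logarithm. A gated fraction cannot be negative.

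**The case against.** **Pooling is not the settled analysis.** It appears only in the power discussion and in conditional language, and every test named for this endpoint is at participant level. A reader might infer that the trial will pool and that type I error will be inflated. The documents do not support that. What stands is the conflict: the plan says it would *revert* from pooling, and nothing says which statement governs.

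**The homogeneity test is assumed.** The plan promises only an evaluation, so the error figures illustrate what such a rule could do. That the error depends on an unstated threshold is itself part of the problem.

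**Section 6.4.4.1 may protect the comparison.** It puts an overall test at 0.05 before the adjacent-pair tests. Adding a three-arm Kruskal-Wallis gate brings the error to 2.1% (10 cells, CV 30%), 2.0% (20 cells, CV 20%) and 2.0% (100 cells, CV 10%). However, that section exempts pre-specified comparisons, and the two Part A comparisons are specified in Section 6.1.2, so whether the gate applies is unclear. The figures in the working leave it out.

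**Normal log rates do not prove that true rates differ.** A reader might infer that the plan refutes its own homogeneity assumption. But the statement concerns preliminary data, in the case where pooling is not justified, and observed rates vary by sampling even when the true rate is common.

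**A larger error figure is available but is not the right summary.** Among simulated trials that keep pooling, the error is about 10%, but these are only about a third of trials. The error of the whole procedure is about 4%.

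**The 0.2% example can be rescued.** If the raw SD were the same in both arms, power would be about 88-97%. But the log-SDs would then differ between arms, and the per-SD argument from log-normality would no longer apply. The text does not say which it means.

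**Conclusion.** Two defects hold. First, Section 6.1.2 gives both a data-driven pooling rule and a participant-level test for one endpoint, without reconciling them. If the pooling rule were used, Part A error would be about 3.4-4.2% or 5-6%, depending on the threshold, against 2.5%. This arises only when between-person variation is moderate and often missed, and before any overall-test gate. Second, the 0.2% example is not on the scale that justifies its power. Under log-normal rates with a common log-SD and one zero per arm, the power is about 42-71% rather than 90% at mean rates of 0.05-0.4%. Cell counts, CVs, the homogeneity test and the mean rates are all assumptions.

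The consequence is limited. This is a secondary endpoint in both parts. Section 4.8.1 rests the dose choice on validated binding-antibody data and uses this assay as an additional input. A reader might infer that one spurious p-value here could set the dose, but no dose rule in the documents depends on it. The stated 80% and 90% power at 1.81 and 2.04 SD is not in question.

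**What to change.** In Section 6.1.2 and the SAP:
- Delete the pooling switch. Make the participant the unit throughout, using the Wilcoxon test already specified on one rate per person. A model with a participant effect would also resolve the conflict.
- Fix one definition of that rate: the gated fraction of memory B cells that bind CH505TF and not the mutant. Keep the two separate binding proportions as descriptive measures.
- Replace the 0.2% example with a fold change in log-SD units. For illustration, 2.04 SD is a 2.6-, 4.1-, 6.3- or 10.5-fold change for assumed log10 SDs of 0.2, 0.3, 0.391 or 0.5. The sponsor should insert the SD from its preliminary data.
- State whether the overall test in Section 6.4.4.1 precedes the two Part A comparisons.

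The cost is wording only. Sample size and stated power do not change, because they already assume participant-level analysis. The downside is that any power gain from pooling is lost if rates really are identical across participants.
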